## Section 5. Privacy and Confidentiality

### ***Data Management:***

**Identifiers:** Given the sensitive nature of this research, the computer software will simply generate a code number for each participant. Data will only be identified with the study’s ID of the participant. Participants will complete the assessments on a VA issued laptop or tablet.

**Confidentiality:** All paper forms (informed consent; HIPPA) with participant information will be marked with a code number and not with the participants’ name. PI [name] and approved CTVHCS study staff will keep the link between the participant code number and name in a password protected master file separate from coded data on the Central Texas secure research (W) drive. The paper files will be stored in locked file cabinet in a locked room at the VHA VISN 17 Center of Excellence in Waco, TX.

No participant will be identified in any publications or presentations arising from this study. Records will be maintained in accordance with the Department of Veterans Affairs Record Control Schedule 10-1. It may be necessary or required for the study investigators to break confidentiality and release personal identifiers and health information when mandated by law. For example, state law requires health care workers to report any suspected abuse or neglect of a child, or person 65 years or older, or an adult with disabilities to the Texas Department of Family and Protective Services.

A Certificate of Confidentiality will be obtained from the National Institutes of Health prior to the commencement of research. The purpose of this certificate is to protect the identity of research subjects participating in studies that collect sensitive information. No information about participants will be released without their permission or where required by law (such as the examples given above). All employees who are to handle data will be trained in confidentiality policies and procedures. In the event that theft, loss, or other unauthorized access of sensitive data and non-compliance with security controls occur, study staff has been instructed to follow the CTVHCS standard operating procedure on incidence reporting.

**Disposition of the data:** Paper files containing identifiers will be kept in locked file cabinets in a locked room at the Center Of Excellence in Waco, TX. Coded paper files will be kept in separate locked file cabinets. Only approved study staff will have access to the files. Electronic data will be stored on the secure VA password-protected server with access restricted

to research staff. Records will be maintained and retained in accordance with the Department of Veterans Affairs Record Control Schedule 10-1.

**Incident Reporting:** Any incidents affecting the security of the data such as theft, loss, or unauthorized access of sensitive data will be reported to the ISO and PO per VA regulations.

## **Section 6. Technical Specifications**

**Survey/Intervention Administration:** Study assessments and intervention sessions will occur only through web administration at in-person sessions held in women's primary care or dedicated research space at the VA in Waco and Temple. We will use the Computerized Intervention Authoring Software (CIAS), developed by [name], and licensed through Interva, Inc. The Computerized Authoring Intervention Software (CIAS) is a sophisticated web-based program designed to allow development and modification of computer-delivered assessment and intervention modules for research studies. This software utilizes SSL technology for encrypting of communications between remote computers and the server itself, and is currently used in a number of major NIH-funded research studies. A license to use the CIAS system will be purchased by grant funds, and no software or data will be downloaded to the VA issued laptop/tablet.

To access the system, investigators and study staff will utilize Kiosk Mode on study laptops or tablets, which will limit participant computer access to a unique and non-searchable FIPS 140-2 compliant study website. Each participant will be set up with the day's screening, assessment or intervention session using only software-generated unique and non-identifying user IDs. No protected health information will be entered into the surveys or interventions.

The intervention and assessment sessions will be constructed by project staff affiliated with the parent site in Providence, RI.

### **Identifiers/linking data:**

No IP addresses or other electronic identifiers will be recorded. Participants will not enter their name or any other identifying information or PHI into the web site. All data storage devices, will be VA issued and monitored by information management services. Only study personnel authorized by the Principal Investigator (PI) will have access to the data, and the file server is protected from the internet by a firewall.

A password protected master participant tracking spreadsheet will contain the linking information that matches the unique participant IDs to participant names. This spreadsheet will reside only on the secure research W drive. Other PHI such as participant addresses and phone numbers (for follow-up contact), and date of participation will be contained in the master tracker. This information will only be accessible to PI [name] and her research staff that is approved to work on the study.

**Data Retrieval:** Data collected through the CIAS system resides on a firewall-protected server in Southfield, Michigan that uses AES-256 encryption in transit. All data will be downloaded from the CIAS server on a weekly basis and stored in a password protected file on the secure central Texas VA research server (W drive) in a restricted folder (e.g. W:\Research

Projects\[name] ). The progress of participants will be closely monitored to ensure that each subject record is erased as quickly as possible. Any staff no longer associated with the study will have access to the study files removed.

**Data Transfer:**

For each participant at the first study visit, the most data to transport would be the informed consent documents for the study. For the interview phase of this study, this will also include recordings of interviews conducted. Study data collected at the Temple campus (informant interviews recordings) will be transported to the approved data storage location at the Waco Campus where it will be uploaded to the secure research W drive. Personally identifying information (e.g. Informed Consent Form with name and date of consent) will be kept in a separate locked carrying case from the data during transport. No other paper data is collected as part of this study. The digital recorder used will be FIPS 140-2 compliant.

De-identified data encrypted via FIPS 140-2 will be transferred to other institutions for data analysis (e.g. Women and Infants Hospital and Brown University) through UPS with a chain of custody. Listed are the following people and addresses that de-identified data will be sent to:

[name]  
Butler Hospital  
[name]  
[name]

The data will not be returned, and will be handled in compliance with VHA's Records Control Schedule (RCS 10-1). All de-identified data will be managed in accordance with the VHA Handbook 1605.1 APPENDIX B.

**Records destruction information:** "Any and all paper AND electronic documentation containing confidential, personally identifiable information, protected health information, and any other sensitive information will be disposed/destroyed according to current VA regulations at the time of disposal/destruction of documentation."

**Records retention information:** "The required records, including the investigator's research records, must be retained until disposition instructions are approved by the National Archives and Records Administration and are published in VHA's Records Control Schedule (RCS 10-1)."

**Reporting:** Any incidents involving theft or loss of data or storage media, unauthorized access of sensitive data or storage devices or non-compliance with security controls will be immediately reported to the IRB chair, Privacy Officer and Information Security Officer.

**Data Analysis Software:** Data will be analyzed using the software programs SPSS and MPLUS that are already owned by the VA either using local copies of the software or through VA Informatics and Computing Infrastructure (VINCI).

**Data use:** Only IRB approved personnel will have access to the data collected in this study. Access to the study data will be terminated when personnel are no longer part of the research

team. De-identified copies of the study datasets will be sent to the parent site. The datasets will be checked by the Privacy Officer before they are sent to the parent site to verify removal of all 18 individually-identifiable information.

**VINCI:** VINCI is a major informatics initiative of the Department of Veterans Affairs (VA) that provides a secure, central analytic platform for performing research and supporting clinical operations activities. It is a partnership between the VA Office of Information Technology (OI&T) and the Veterans Health Administration Office of Research and Development (VHA ORD). VINCI includes a cluster of servers for securely hosting suites of databases integrated from select national VA data sources. VINCI servers for data, applications and virtual sessions are physically located at the VA Austin Information Technology Center (AITC), located in Austin, Texas. This secure enclave with 105 high-performance servers and 1.5 petabytes of high-speed data storage has multiple layers of security and disaster recovery to prevent data loss.

To ensure the protection of Veteran data, VINCI maintains compliance with the guidelines set forth by Veterans Health Administration (VHA) Handbook 1200.12, Use of Data and Data Repositories in VHA Research, and all other applicable VA and VHA policies and regulations. In addition, VINCI has undergone all security certification activities in support of obtaining an Authorization to Operate (ATO). Access to VINCI resources are approved in accordance with the requirements of National Data Systems (NDS), VHA Handbook 1200.12, Use of Data and Data Repositories in VHA Research, and all other applicable VA and VHA policies and regulations. All data transferred from VINCI is subject to audit for compliance.

VA-credentialed research or operations staff are granted access to study-specific data along with tools for analysis and reporting in the secure, virtual working environment through a certified VHA network computer within the VA. If not working within a VA or VHA hosted office environment containing VA network access, researchers may apply for and then access VINCI through an approved Virtual Private Network (VPN) and Remote Desktop application. The remote computing environment enables data analysis to be performed directly on VINCI servers, offering a number of advantages: uniform security standards for access; a common point of entry for all investigators who use the data; tools for analysis and reporting; tighter and more consistent control of data quality; and the ability to standardize and update terminology and format as technology and methodology improve.

Only study team personnel explicitly authorized by data stewards will have access to project data. The study principal investigator has the responsibility for security of study. VINCI data managers and VA OI&T personnel not under the purview of the study principal investigator control the servers, network, processors, firewall and software in the VINCI environment, including access rights granted to study personnel.

When study personnel are no longer part of the research team, the study principal investigator will amend the data access request to terminate that person's access to all study data and notify the VA Information Security Officer of such action. No sensitive patient data may be shared with anyone who does not have a VA appointment. All study team personnel with access to sensitive patient data must stay current on required VA information security and privacy policy trainings.

Study data stored on VINCI servers is located at the Austin Information Technology Center, [name]. The specific server where the data are stored within the VINCI environment will be chosen by VINCI personnel. The server name and location within the Austin Information Technology Center may be changed at any time at the discretion of VINCI personnel.

## **Section 7. Data Safety and Monitoring**

### ***Safety monitoring plan***

**Frequency of DSM:** In this study, we will use the FDA definition of serious adverse events (SAEs). RAs will report SAEs to the PI immediately. Data and safety of patients will be monitored by PI [name]. At a weekly meeting attended by PI [name], study staff, participants' safety, participants' clinical status and adverse experiences will be reviewed. Entrance criteria of all participants will also be reviewed at these meetings. The PI will ensure that information on participants' adverse effects are systematically collected and evaluated.

[name] will immediately report any serious adverse events that are observed to the DSMB, medical monitor, Central Texas VAHCS IRB, and to the U.S. Army Medical Research and Materiel Command's (USAMRMC) Human Research Protection Office (HRPO). The initial SAE report will be followed by submission of a completed SAE report to the local IRB and HRPO. Outcomes of SAEs will be periodically reported to HRPO. A summary of the SAEs that occurred during the previous year will be included in the Quarterly Technical Progress Report that is submitted to HRPO.

A Data and Safety Monitoring Board (DSMB) will be assembled to evaluate the data and safety to women veterans enrolled in the study. The DSMB will consist of 4 senior doctoral-level/MD board members who have experience in clinical trials and/or alcohol/IPV/PTSD intervention research and/or research with women veterans as well as the ethical issues involved with a randomized controlled study, as indicated by peer-reviewed journal articles in these areas. We do not anticipate any difficulty in recruiting these qualified, independent board members as there is a pool of such researchers at the Providence, RI site and at the Central Texas site who have the relevant experience.

The DSMB will convene twice in Year 1, and then once during Year 2 for a meeting. Initially, the Board will convene with the PI [name] and PI [name] to review the study protocol and review the guidelines for data and safety monitoring. This will include establishing standard procedures for daily (whenever there has been contact with a participant) and weekly monitoring by the local internal reviewers (PI and study personnel). At this meeting and at each subsequent meeting, the DSMB will evaluate recruitment, the progress of the trial, subject retention, data quality and confidentiality. In addition, they will review participants' clinical status, rates of adverse events and whether or not there have been any changes in risk to participating subjects. This review will ensure that subject risk does not outweigh study benefits. In the DSMB's review of adverse events, if non-serious adverse events are occurring at a significantly higher rate in one condition than the other, then the DSMB will make appropriate recommendations for changes in the protocol, if needed. If Serious Adverse Events (SAEs) occur at a significantly higher rate in one condition than the other, then the DSMB might consider terminating the trial, if changes to

the protocol are unlikely to address the high occurrence of the SAEs. We do not anticipate that this will occur, because we have taken several steps to avoid or protect against the occurrence of SAEs as outlined in the Human Subject Recruitment and Safety Procedures section. A report generated from each of these meetings will be retained at the study site and will be forwarded to the local IRBs, USAMRAA, and will be included in the Quarterly Technical Progress Report.

The DSMB will be available to convene outside of the appointed meeting schedule, if necessary, due to concerns regarding a particular subject, or due to any troublesome developments in subjects' experiences during the study. The DSMB will make appropriate recommendations for changes in the study protocol, if needed. The safety of participants will be monitored during each contact with study participants. Both anticipated and unanticipated adverse events and problems will be formally monitored and recorded. Unanticipated serious adverse events or problems will be reported to the DSMB, medical monitor, within 24 hours.

A Medical Monitor will be appointed to this study. This individual will not otherwise be associated with this protocol, and will be able to provide appropriate medical care to research volunteers for conditions that may arise during the conduct of the study. Adverse experiences that are both serious and unexpected will be immediately reported by telephone to the U.S. Army Medical Research and Materiel Command's (USAMRMC) Human Research Protection Office (HRPO). A written report will follow the initial telephone call within 3 working days to the U.S. Army Medical Research and Materiel Command and to the appropriate local Institutional Review Boards (IRBs). The Medical Monitor is required to review all serious and unexpected adverse events (per ICH definitions) associated with the protocol, and provide an unbiased written report of the event within 10 calendar days of the initial report to the addresses above.

All study personnel and investigators will annually complete the required VA training and courses in human participant research protections. PI [name] will maintain documentation of human research training requirement for all study personnel and submit the required information and training certificates to the VA Research Office with every new protocol submission. All investigators at both sites are certified in human subjects education by their respective institutions. Monitoring of safety in the proposed study will be the responsibility of all personnel on the project, with primary responsibility and supervision by [name]. The Institutional Review Board at the Central Texas VAHCS will approve the protocol and the Statement of Informed Consent for the study and will provide oversight of data and safety issues. Separate reviews of the protocol and consent form are made by the safety officer at the VA Medical Center. The study protocol will receive IRB approval prior to soliciting or requesting consent from any participants. Moreover, the study will be reviewed on an annual basis (continuing review) by the IRB committee with regard to recruitment and retention and annual reports will be made by the PI to the IRB chair of the Central Texas VAHCS regarding the progress of the proposed project, including any issues pertinent to recruitment, retention, confidentiality, and safety of human subjects. Any incidents that involve a breach of this plan or serious accident/injury will be reported to the IRB chair. As discussed, potential risks, albeit minimally likely, include distress or discomfort with questions regarding trauma history.

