For participants in the trial, we will also conduct a chart review using the VA Computerized Patient Records System to assess for mental health appointment attendance before and after the trial. This will entail documenting the number of mental health appointments attended at VA 4 months before the trial and 4 months after. The purpose of this information is to objectively document whether SHE increases engagement in VHA mental healthcare.

**Assessment of acceptability:** Satisfaction with CIAS Software Scale (SCSS) assesses participant satisfaction on items tapping on likeability, ease of use, level of interest, and respectfulness using a 1 – 5 Likert scale (1 = low, and 5 = high). This scale will be administered after every SHE module. The Client Satisfaction Questionnaire (CSQ) is an 8-item questionnaire which assesses the participant’s satisfaction with the intervention. The scale has good psychometric properties and correlates highly with other intervention measures. Only participants in SHE will complete these two measures immediately after the intervention.

**Measures of family and relationship functioning:** Prior research on Veterans has suggested that family and relationship functioning may influence treatment engagement, therefore we will include such measures as a covariate in analyses and to examine how family functioning may predict treatment completion, appointment attendance. The Quality of Marriage Index (QMI; Norton, 1983) will be used to assess relationship distress (6 items). The Family Assessment Device 12 (FAD; Epstein, Baldwin, Bishop) is a brief measure of general family functioning.

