The investigators' experience with empirically tested programs that address alcohol use, IPV, and/or PTSD will also inform the development of SHE. More specifically, regarding brief MI-based interventions for alcohol, [name] has developed and tested MI based interventions that address heavy drinking and alcoholism. [name] has adapted the proposed study software to screen and intervene with alcohol misuse in a sample of urban, high-risk pregnant population. [name] has successfully developed and tested empowerment based interventions for women with IPV and women with PTSD. [name] is an expert in mental health and sexual trauma among women Veterans and women Veterans issues, as well as in intimate partner violence among Veterans and military populations.

All SHE sessions will take place within the primary care clinic setting or designated research space and consist of three computer delivered intervention modules, each designed to be completed in approximately 30 minutes and tailored to the current risk profile of each participant. The first intervention module will take place after the baseline assessment and remaining modules, if needed, will be given at a session within one week after the first session. Each module will be designed so that it can be administered individually, or in tandem with the other modules. Women will complete only the modules aligning with their risk profile. During the development phase, we will explore various orderings of the modules (i.e., alcohol module

prior to IPV module) so that all women receiving more than one module receive the information in the same order.

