**3.** We will minimize the risk of distress. Participants from our target population face the risk of increased distress during assessment procedures, during the control condition, or during the experimental condition. The potential that veterans might develop uncomfortable feelings during assessments and the intervention will be discussed during the consent process. Possible distress due to sensitive items will be noted clearly in the informed consent information sheet (for screening) and in the written informed consent form (for participants). Participants will be informed that they can refuse to answer any question or stop the assessment or intervention at any time. They will be informed that they can choose to resume the assessment or intervention or refuse to participate further. Veterans will have the opportunity to discuss any uncomfortable feelings with the assessment or intervention with the research assistant who will be available during both the computer-based assessment and intervention. Moreover, clinical backup will be provided during all assessments and during the intervention phase of the study by a licensed clinician to help facilitate any stabilization and referral process for participants who decompensate during study procedures. The need for additional services will also be monitored during all follow-up assessments. The veteran will also be informed that the veteran's well-being and safety takes priority over research considerations. Furthermore the veteran will be informed that should she experience any problems, she should report them to the research assistant or to the principal investigator of this study.

To further address possible distress due to sensitive items, participants will be asked by the computer program if anything the computer has asked or done is making them feel upset right now. The computer program will notify the research team at completion of the screening, intervention session, or assessment, if any participant answers yes to this question, in addition to notifying the research assistant (RA) if the participant endorsed any items indicative of possible need/desire for further assistance. (Note that the computer program will not provide details regarding any answers, only that there is a need to follow-up with the participant verbally to evaluate the need for assistance). At a minimum, all participants indicating some distress will be given a list of referral and resource options.

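### Adverse events are captured through contact or self-report with no common question or look-back, so the DSMB's comparison of non-serious events risks unequal ascertainment, and serious events in women lost to follow-up can go unrecorded

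*Combined protocol and SAP*

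**What the plan says.** **How events are found.** The Safety monitoring plan (Section 7) ties capture to contact: "The safety of participants will be monitored during each contact with study participants". Internal review is "daily (whenever there has been contact with a participant) and weekly monitoring by the local internal reviewers". The same section promises systematic collection and formal recording of events, but describes no instrument, question or recall period. Table 1 (Schedule of Assessment Measures) lists no adverse-event measure.

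**The distress prompt.** Under Risks/Benefits Assessment, item 3, the software asks whether anything it has asked or done is upsetting the woman at that moment. If she says yes: "The computer program will notify the research team at completion of the screening, intervention session, or assessment". Women are also told to report problems to the staff themselves.

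**Who has which contacts.** Section 4 (SHE Intervention) says: "The first intervention module will take place after the baseline assessment and remaining modules, if needed, will be given at a session within one week". The Control section offers screening and referral only. Both arms have assessments at 2 and 4 months. The Retention section allows these by phone, and item 4 of the risk section has safe-contact details updated monthly.

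**What the DSMB does with the events.** It considers changes to the protocol "if non-serious adverse events are occurring at a significantly higher rate in one condition than the other". For serious events that differ in the same way, "then the DSMB might consider terminating the trial" if changes to the protocol are unlikely to help. No test, significance level or denominator is given.

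**Records.** The chart review in Section 3 (Assessment of treatment utilization) covers all trial participants, but only for "documenting the number of mental health appointments attended at VA 4 months before the trial and 4 months after".

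**The concern.** A between-arm comparison of event rates is interpretable only if both arms are asked the same thing, equally often, over the same period. Here one arm has sessions that the other lacks, each is an occasion to notice or elicit an event, and nothing in the plan equalizes the two. With no true difference, non-serious events could be recorded more often in SHE simply because staff and software ask more often. The DSMB is asked to act on that contrast.

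The second gap does not depend on arm. Adverse Event Reporting names suicide attempts and inpatient hospitalization as examples of serious events. The protocol names no source for such events in women who cannot be reached, although staff will already be opening their VA records. The safety data are part of the groundwork for a larger trial, so incomplete capture would carry forward.

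**Working it through.** The documents give no contact count, event rate or power for the safety comparison, so there is no stated figure to reproduce.

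**Inputs from the plan**
- Risk mix: 50/50/50 women with 1, 2 and 3 risks (Power Analysis).
- Modules: one per risk (SHE Intervention).
- Follow-up assessments: 2 per arm.
- Retention: 126 of 155 (Power Analysis).
- Allocation: about half per arm, taken as 78 SHE and 77 control.

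**Step 1: contacts after randomization.** Mean SHE contacts = 2 + average module sessions over the three risk groups + any monthly contacts. Control = 2 + the same monthly contacts. If module 1 is its own contact and the remaining modules share one session, SHE = 2 + (1 + 2 + 2)/3 = 3.67, and 3.67/2 = 1.83. The other counts follow in the same way. The columns give the ratio with 0, 2 or 4 monthly contacts added to each arm:

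| Count of module sessions (1/2/3 risks) | +0 | +2 | +4 |
|---|---|---|---|
| Module 1 separate, rest in one session (1, 2, 2) | 1.83 | 1.42 | 1.28 |
| One visit per module (1, 2, 3) | 2.00 | 1.50 | 1.33 |
| Module 1 within baseline visit, rest in one session (0, 1, 1) | 1.33 | 1.17 | 1.11 |
| Module 1 within baseline visit, one visit per further module (0, 1, 2) | 1.50 | 1.25 | 1.17 |

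The range is 1.11 to 2.00. For the distress prompt alone, the first row without monthly contacts fits best: the prompt follows each intervention session, and the monthly updates are described as checking contact details, not as eliciting events.

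**Step 2: timing.** All the extra SHE contacts fall in the first week: 7/122 days = 5.7% of four months. Scheduled contacts are equal afterwards.

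**Step 3: illustration only.** Assume that each contact has probability p of yielding a recorded event, independently and equally in both arms. A woman with k contacts then has at least one event with probability 1 − (1 − p)^k. The test assumed is a two-sided Fisher test at .05, counting only results against SHE.

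Worked for p = .05 and the 1.83 count: control 1 − .95² = 9.8%; SHE (1/3)(1 − .95³) + (2/3)(1 − .95⁴) = 17.1%. For p = .10: 19.0% and 32.0%.

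| Contact ratio | Signal against SHE, p = .05 | p = .10 |
|---|---|---|
| 1.83 | 21.1% | 41.2% |
| 1.42 (two monthly contacts added) | 13.6% | 23.9% |
| 1.33 (module 1 within baseline) | 5.8% | 9.9% |
| 1.17 (both) | 4.6% | 7.0% |
| 1.00 (two contacts per arm) | 1.5% | 1.7% |

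The direction is the same in every row, but the size moves with the count and with p. The documents fix neither.

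**Step 4: loss.** 155 − 126 = 29; 29/155 = 18.7%. No split by arm is given.

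**The case against.** A reader might infer that events are recorded only at meetings, that SHE women have nearly twice the contacts, and that the DSMB comparison is therefore biased against SHE by a known amount. The documents do not support that.

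- **Capture is wider than meetings.** Follow-ups may be by phone, contact details are updated monthly, and women are told to report problems themselves. Staff also pursue follow-up whether or not the intervention was completed.
- **Nearly twice is the upper part of a range** that goes down to 1.11.
- **The signal rates in Step 3 are not estimates.** The prompt concerns distress from that session. A yes after a module is partly a true SHE effect that a control woman cannot have, so assuming no true difference overstates the artefact. No section says that a yes is logged as an adverse event. Independence across a woman's contacts, the test and the level are all assumptions.
- **Serious events are little affected.** A few extra contacts in week 1 should hardly change the recording of hospital admissions, and the termination wording is discretionary. The board can see that modules exist in one arm only.
- **Loss has no known direction.** It supports no claim of bias for or against SHE, and some of the 29 may still have had contact before month 4.

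All of this stands, and it limits the point to a risk. It does not supply what is missing: a common question, a common look-back and a source for unreachable women. The general promise of systematic collection, and the plan to settle monitoring procedures at the first DSMB meeting, leave both arms' ascertainment undefined in the protocol.

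**Conclusion.** The point holds as a risk of differential ascertainment in the between-condition comparison of non-serious events, mainly distress in week 1. The contact ratio is 1.11 to 2.00 under the projected 50/50/50 mix. How far this would distort the comparison cannot be determined, because the plan gives no event rate, test or rule for what counts as an event. If staff in fact asked at each contact about the whole interval since the last one, most of the difference would disappear after week 1; the plan does not say that they will.

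Separately, serious events can be missed in either arm among the 18.7% of women expected to be lost. That rests only on the plan's own retention figure and on the absence of a named source, and it carries no known direction of bias. Both are worth correcting because the correction is cheap.

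**What to change.** 1. **Common question.** In the Safety monitoring plan, specify one identical adverse-event question at the 2- and 4-month assessments in both arms, covering the time since the last assessment. Make it the main basis for the DSMB's between-condition comparison.
2. **Module-session distress.** Label distress flagged at SHE module sessions by source and report it per session beside that comparison, so that the board still sees and weighs it. Removing it would hide the events that SHE is most likely to cause.
3. **Chart review.** Extend the planned CPRS review to hospital admissions, emergency visits and recorded suicide attempts over the same 4 months for every randomized woman, including those lost to follow-up, as HIPAA authorization and consent allow. State that the window starts at randomization.

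**Cost.** Protocol wording, a short item in the existing follow-up assessments, a few more abstraction fields, and matching consent and authorization text. CPRS shows VA care only, so events treated elsewhere would still be missed. The look-back relies on recall of up to two months, and abstraction takes somewhat longer.
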